##### 4.9.1 Pneumonitis:

- For **Grade 2 events**, treat with systemic corticosteroids. When symptoms improve to Grade 1 or less, steroid taper should be started and continued over no less than 4 weeks.
- For **Grade 3-4 events**, immediately treat with intravenous steroids. Administer additional anti-inflammatory measures, as needed.
- Add prophylactic antibiotics for opportunistic infections in the case of prolonged steroid administration.

##### 4.9.2 Diarrhea/Colitis:

Subjects should be carefully monitored for signs and symptoms of enterocolitis (such as diarrhea, abdominal pain, blood or mucus in stool, with or without fever) and of bowel perforation (such as peritoneal signs and ileus).

- All subjects who experience diarrhea/colitis should be advised to drink liberal quantities of clear fluids. If sufficient oral fluid intake is not feasible, fluid and electrolytes should be substituted via IV infusion. For Grade 2 or higher diarrhea, consider GI consultation and endoscopy to confirm or rule out colitis.
- For **Grade 2 diarrhea/colitis** that persists greater than 3 days, administer oral corticosteroids.

- For **Grade 3 or 4 diarrhea/colitis** that persists > 1 week, treat with intravenous steroids followed by high dose oral steroids.
- When symptoms improve to Grade 1 or less, steroid taper should be started and continued over no less than 4 weeks.

**4.9.3 Type 1 diabetes mellitus (if new onset, including diabetic ketoacidosis [DKA]) or  $\geq$  Grade 3 Hyperglycemia, if associated with ketosis (ketonuria) or metabolic acidosis (DKA)**

For **T1DM** or **Grade 3-4** Hyperglycemia

- Insulin replacement therapy is recommended for Type I diabetes mellitus and for Grade 3-4 hyperglycemia associated with metabolic acidosis or ketonuria.
- Evaluate patients with serum glucose and a metabolic panel, urine ketones, glycosylated hemoglobin, and C-peptide.

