### **4.3 Dose Modifications**

#### **4.3.1 Dose Modification**

Adverse events (both non-serious and serious) associated with pembrolizumab exposure may represent an immunologic etiology. These adverse events may occur shortly after the first dose or several months after the last dose of treatment. Pembrolizumab must be withheld for drug-related toxicities and severe or life-threatening AEs as per Table 1 below. Dose reductions for pembrolizumab are not permitted.

Capecitabine should be withheld/dose reduced for drug-related toxicities and AEs as per Table 2, 3, 4.

See Section 4.9 for supportive care guidelines for pembrolizumab, including use of corticosteroids.

Any patient who receives at least one dose of study therapy will be evaluable for toxicity endpoints. Each patient will be assessed for the

development of toxicity according to the timeframe referenced in the Schedule of Events table). Toxicity will be assessed according to NCI's CTCAE, version 4.03.

Dosing interruptions are permitted in the case of medical / surgical events or logistical reasons not related to study therapy (e.g., elective surgery, unrelated medical events, patient vacation, and/or holidays). Subjects should be placed back on study therapy within 3 weeks of the scheduled interruption of capecitabine and 12 weeks of interruption of pembrolizumab, unless otherwise discussed with the Principal Investigator and QAM. The reason for interruption should be documented in the patient's study record.

If pembrolizumab is held for toxicity, participants are permitted to continue on protocol therapy with capecitabine alone. If capecitabine is held for toxicity, participants are permitted to continue on therapy with pembrolizumab alone.

If capecitabine doses are missed, and it is < 7 doses, they may be made up within the same cycle.

If one drug is permanently withdrawn for toxicity (i.e. the patient cannot dose reduce any further on capecitabine), then the patient should come off study completely.

Capecitabine Dose Reduction Table

Dose Level	Dose
1	1000 mg/m 
-1	800 mg/m 
-2	640 mg/m 
Stop	N/A

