**Table 1 –Dose Modification and Toxicity Management Guidelines for Immune-related AEs Associated with Pembrolizumab**

General instructions:				

 
1. Corticosteroid taper should be initiated upon AE improving to Grade 1 or less and continue to taper over at least 4 weeks.
 
2. For situations where pembrolizumab has been withheld, pembrolizumab can be resumed after AE has been reduced to Grade 1 or 0 and corticosteroid has been tapered. Pembrolizumab should be permanently discontinued if AE does not resolve within 12 weeks of last dose or corticosteroids cannot be reduced to <math>\leq 10</math> mg prednisone or equivalent per day within 12 weeks.
 
3. For severe and life-threatening irAEs, IV corticosteroid should be initiated first followed by oral steroid. Other immunosuppressive treatment should be initiated if irAEs cannot be controlled by corticosteroids.
 
				
Immune-related AEs	Toxicity grade or conditions (CTCAEv4.0)	Action taken to pembrolizumab	irAE management with corticosteroid and/or other therapies	Monitor and follow-up
Pneumonitis	Grade 2	Withhold	
 
• Administer corticosteroids (initial dose of 1-2 mg/kg prednisone or equivalent) followed by taper
 
	
 
• Monitor participants for signs and symptoms of pneumonitis
 
• Evaluate participants with suspected pneumonitis with radiographic imaging and initiate corticosteroid treatment
 
• Add prophylactic antibiotics for opportunistic infections
 

	Grade 3 or 4, or recurrent Grade 2	Permanently discontinue		

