Diarrhea / Colitis	Grade 2 or 3	Withhold	
 
• Administer corticosteroids (initial dose of 1-2 mg/kg prednisone or equivalent) followed by taper
 
	
 
• Monitor participants for signs and symptoms of enterocolitis (ie, diarrhea, abdominal pain, blood or mucus in stool with or without fever) and of bowel perforation (ie, peritoneal signs and ileus).
 
• Participants with <math>\geq</math> Grade 2 diarrhea suspecting colitis should consider GI consultation and performing endoscopy to rule out colitis.
 
• Participants with diarrhea/colitis should be advised to drink liberal quantities of clear fluids. If sufficient oral fluid intake is not feasible, fluid and electrolytes should be substituted via IV infusion.
 

	Grade 4	Permanently discontinue		
AST / ALT elevation or Increased bilirubin	Grade 2	Withhold	
 
• Administer corticosteroids (initial dose of 0.5- 1 mg/kg prednisone or equivalent) followed by taper
 
• Administer corticosteroids (initial dose of 1-2 mg/kg prednisone or equivalent) followed by taper
 
	
 
• Monitor with liver function tests (consider weekly or more frequently until liver enzyme value returned to baseline or is stable)
 

	Grade 3 or 4	Permanently discontinue		

Type 1 diabetes mellitus (T1DM) or Hyperglycemia	Newly onset T1DM or Grade 3 or 4 hyperglycemia associated with evidence of $\beta$ -cell failure	Withhold	
 
Initiate insulin replacement therapy for participants with T1DM
 
Administer anti-hyperglycemic in participants with hyperglycemia
 
	
 
Monitor participants for hyperglycemia or other signs and symptoms of diabetes.
 

Hypophysitis	Grade 2	Withhold	
 
Administer corticosteroids and initiate hormonal replacements as clinically indicated.
 
	
 
Monitor for signs and symptoms of hypophysitis (including hypopituitarism and adrenal insufficiency)
 

	Grade 3 or 4	Withhold or permanently discontinue 		

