#### 4.9 Supportive Care Guidelines & Toxicity Management

Subjects should receive appropriate supportive care measures as deemed necessary by the treating investigator. Suggested supportive care measures for the management of adverse events with potential immunologic etiology are outlined below. Where appropriate, these guidelines include the use of oral or intravenous treatment with corticosteroids as well as additional anti-inflammatory agents if symptoms do not improve with administration of corticosteroids. Note that several courses of steroid tapering may be necessary as symptoms may worsen when the steroid dose is decreased. For each disorder, attempts should be made to rule out other causes such as metastatic disease or bacterial or viral infection, which might require additional supportive care. Toxicity will be attributed to either or both drugs per physician's clinical judgement, and dose modifications/delays will be made accordingly.

Note: if after the evaluation the event is determined not to be related, the investigator is instructed to follow the treatment guidance (as outlined below)

It may be necessary to perform conditional procedures such as bronchoscopy, endoscopy, or skin photography as part of evaluation of the event. Refer section 4.3 for dose modification.

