**4.9.6 Hepatic:**

- For **Grade 2** events, monitor liver function tests more frequently until returned to baseline values (consider weekly).
- Treat with IV or oral corticosteroids
- For **Grade 3-4** events, treat with intravenous corticosteroids for 24 to 48 hours.
- When symptoms improve to Grade 1 or less, a steroid taper should be started and continued over no less than 4 weeks.

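### Section 4.9.2 makes steroids for diarrhea/colitis wait on persistence and the Table 1 row does not; the conflict is clear for Grades 2 and 3, and no text says which rule governs

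*Combined protocol and SAP*

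**What the plan says.** Section 4.9.2 of the combined protocol and SAP makes steroid treatment depend on grade and on duration. For a Grade 2 event "that persists greater than 3 days, administer oral corticosteroids". For a Grade 3 or 4 event "that persists > 1 week, treat with intravenous steroids followed by high dose oral steroids".

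Table 1 in Section 4.3.1 has its own diarrhea/colitis row and its own corticosteroid column. Pembrolizumab is withheld at Grade 2 or 3 and stopped permanently at Grade 4. The steroid entry on the Grade 2 or 3 line reads "Administer corticosteroids (initial dose of 1-2 mg/kg prednisone or equivalent) followed by taper". General instruction 3 at the head of the table adds: "For severe and life-threatening irAEs, IV corticosteroid should be initiated first followed by oral steroid".

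The two places refer to each other. Section 4.3.1 says "See Section 4.9 for supportive care guidelines for pembrolizumab, including use of corticosteroids", and Section 4.2.1 says the same. Section 4.9 refers back to Section 4.3, but only for dose modification. Section 4.9 describes its own status this way: "Suggested supportive care measures for the management of adverse events with potential immunologic etiology are outlined below".

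**The concern.** A physician treating immune-related colitis can follow the protocol's own pointer to Section 4.9.2 and find a waiting period that Table 1 does not contain. The wait is longer for the severe grades than for Grade 2. Section 4.9.2 itself asks physicians to watch for bowel perforation, so a delayed start is a patient-safety matter.

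The wait also stands out within Section 4.9. For Grade 3-4 pneumonitis, Section 4.9.1 says "immediately treat with intravenous steroids. Administer additional anti-inflammatory measures, as needed". For Grade 3-4 hepatic events, Section 4.9.6 says "treat with intravenous corticosteroids for 24 to 48 hours". Neither sets a minimum duration before steroids begin.

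**Working it through.** The plan gives no figure to reproduce and no formula applies. The check sets the texts side by side.

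| Grade | Section 4.9.2: steroids start | Table 1: steroids start | Conflict |
|---|---|---|---|
| 2 | after more than 3 days | diarrhea/colitis row: no wait stated | clear |
| 3 | after more than 1 week | diarrhea/colitis row: no wait stated | clear |
| 4 | after more than 1 week | row's cell unclear in the text available; general instruction 3 states no wait | probable |

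**Step 1, a test case.** Take Grade 3 immune-related colitis on day 2. It meets the steroid direction in the Table 1 row. It does not meet the one in Section 4.9.2, which is first met after day 7, so more than 7 - 2 = 5 further days pass. The severe-grade wait exceeds the Grade 2 wait by 7 - 3 = 4 days.

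**Step 2, Grade 4.** In the available text the steroid entry stands on the Grade 2 or 3 line and nothing stands on the Grade 4 line. A merged cell is likely but cannot be confirmed. General instruction 3 does reach Grade 4, but its wording mainly sets a sequence, IV and then oral. Section 4.9.2 has the same sequence at Grade 3-4. What remains is that instruction 3 states no wait and Section 4.9.2 states one.

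**Step 3, is there a ranking?** The mandatory wording in Section 4.3.1 concerns withholding pembrolizumab, not steroid timing. Table 1 calls itself guidelines and Section 4.9 calls its measures suggested, so neither label outranks the other. The cross-references do not settle the order.

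**Step 4, is the wait usual within Section 4.9?** Six subsections direct steroids by grade: 4.9.1, 4.9.2, 4.9.4, 4.9.5 (Grade 3-4 hyperthyroidism), 4.9.6 and 4.9.7. One of the six, 4.9.2, has a persistence condition. Not counted are 4.9.3 and 4.9.8 (no steroid direction), 4.9.9 (no grade given) and 4.9.10 (infusion reactions, which Section 8.1.10 does not regard as immune mediated).

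**Step 5, how many patients?** Section 8.1.10 places colitis of any grade, inflammatory or infectious, at 1 to 10% with pembrolizumab. If that range applied to the 30 planned patients, it would be 30 × 0.01 = 0.3 to 30 × 0.10 = 3 patients. The documents give no rate for Grade 3-4 immune-related colitis, so no expected number of delayed treatments follows.

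**The case against.** The strongest defence is that the two texts differ in scope. Table 1 is titled for immune-related events. Section 4.9 covers events of possible immune origin, asks that other causes be excluded, and lets the physician attribute toxicity to either drug. Its note on events found to be unrelated carries it further still. Capecitabine commonly causes diarrhea (Section 8.2.10) and has its own hold rule in Table 3, and Section 4.4 restricts systemic steroids to suspected immune events. A period of observation is therefore reasonable in this regimen. On this reading Section 4.9.2 applies while the cause is open and Table 1 applies once it is known.

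Part of this stands. Observation is justified while diarrhea is attributed to capecitabine or unexplained, and the 1-of-6 count alone proves no error. The division of scope does not hold, however. The Table 1 row itself covers diarrhea with suspected colitis and mentions endoscopy to exclude it. Section 4.9.2 names colitis and does not end the wait once colitis is confirmed. Table 3 says nothing about steroids and has no Grade 4 diarrhea line.

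A second defence is that Table 1 is merely silent on timing. That has force for general instruction 3. It has less force for the row, which directs steroids at Grade 2 or 3 without any condition, whereas Section 4.9.2 attaches one.

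Third, Section 4.9 leaves care to the investigator's judgment, and other protections do not depend on it: Table 1 withholds or stops pembrolizumab with no wait, and capecitabine is held at Grade 3 diarrhea. This is correct and limits the severity. A reader might infer that Section 4.9.2 forbids earlier steroids. It does not.

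**Conclusion.** The inconsistency is real and lies in current text. Section 4.9.2 conditions steroids on persistence, the Table 1 row does not, and no sentence says which prevails. The difference is more than 3 days at Grade 2 and more than 1 week at Grade 3. It should be corrected for patient safety. It has no bearing on sample size, power or the PFS analysis.

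Two stronger readings are tempting. The first is that the conflict is established through Grade 4. The documents make it probable only, for the reasons in Step 2. The second is that Table 1 should simply override Section 4.9 on steroids. That goes too far: for Grade 3-4 hyperthyroidism Section 4.9.5 directs IV and then oral steroids, while the Table 1 row lists only beta-blockers or thionamides, so a general override could cancel a direction that this point gives no reason to remove.

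The amendment history records that Amendment 6 replaced Table 1 and lists no matching change to Section 4.9. That suggests how the mismatch arose, but the conclusion does not rest on it.

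**What to change.** In Section 4.9.2, remove the 3-day and 1-week conditions for diarrhea/colitis judged or suspected to be immune-related, so that steroids start as in Table 1, with the IV route first for Grade 3-4. Keep an observation period only for diarrhea attributed to capecitabine or whose cause is still under evaluation. State that the wait ends as soon as an immune cause is suspected or confirmed.

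If a precedence sentence is preferred, confine it to this topic, for example: where Section 4.9.2 and Table 1 differ on steroid treatment of immune-related diarrhea/colitis, Table 1 applies. It should not extend to the rest of Section 4.9. In either case, state explicitly in Table 1 that the diarrhea/colitis steroid entry covers Grade 4, if that is intended.

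The cost is a wording amendment and a notice to treating physicians at the single center.

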**4.9.4 Hypophysitis:**

- For **Grade 2** events, treat with corticosteroids. When symptoms improve to Grade 1 or less, steroid taper should be started and continued over no less than 4 weeks. Replacement of appropriate hormones may be required as the steroid dose is tapered.
- For **Grade 3-4** events, treat with an initial dose of IV corticosteroids followed by oral corticosteroids. When symptoms improve to Grade 1 or less, steroid taper should be started and continued over no less than 4 weeks. Replacement of appropriate hormones may be required as the steroid dose is tapered.

**4.9.5 Hyperthyroidism or Hypothyroidism:**

Thyroid disorders can occur at any time during treatment. Monitor patients for changes in thyroid function (at the start of treatment, periodically during treatment, and as indicated based on clinical evaluation) (see section 5.0) and for clinical signs and symptoms of thyroid disorders.

- **Grade 2** hyperthyroidism events (and **Grade 2-4** hypothyroidism):
  - In hyperthyroidism, non-selective beta-blockers (e.g. propranolol) are suggested as initial therapy.
  - In hypothyroidism, thyroid hormone replacement therapy, with levothyroxine or liothyronine, is indicated per standard of care.
- **Grade 3-4** hyperthyroidism
  - Treat with an initial dose of IV corticosteroid followed by oral corticosteroids. When symptoms improve to Grade 1 or less, steroid taper should be started and continued over no less than 4 weeks. Replacement of appropriate hormones may be required as the steroid dose is tapered.

**4.9.6 Hepatic:**

- For **Grade 2** events, monitor liver function tests more frequently until returned to baseline values (consider weekly).
- Treat with IV or oral corticosteroids
- For **Grade 3-4** events, treat with intravenous corticosteroids for 24 to 48 hours.
- When symptoms improve to Grade 1 or less, a steroid taper should be started and continued over no less than 4 weeks.

**4.9.7 Renal Failure or Nephritis:**

- For **Grade 2** events, treat with corticosteroids.
- For **Grade 3-4** events, treat with systemic corticosteroids.

When symptoms improve to Grade 1 or less, steroid taper should be started and continued over no less than 4 weeks.

#### **4.9.8 Stevens-Johnson Syndrome(SJS) and Toxic Epidermal Necrolysis(TEN)**

- For signs or symptoms of SJS or TEN, withhold pembrolizumab and refer the patient for specialized care for assessment and treatment.
- If SJS or TEN is confirmed, permanently discontinue pembrolizumab.

#### **4.9.9 Immune-mediated myocarditis**

- For suspected immune-mediated myocarditis, ensure adequate evaluation to exclude other etiologies, and administer corticosteroids as appropriate.

#### **4.9.10 Management of Infusion Reactions:**

Signs and symptoms usually develop during or shortly after drug infusion and generally resolve completely within 24 hours of completion of infusion. **Table 5** below shows treatment guidelines for subjects who experience an infusion reaction associated with administration of pembrolizumab (MK-3475).

**Table 5 Infusion Reaction Treatment Guidelines**

NCI CTCAE Grade	Treatment	Premedication at subsequent dosing
Grade 1 Mild reaction; infusion interruption not indicated; intervention not indicated	Increase monitoring of vital signs as medically indicated until the subject is deemed medically stable in the opinion of the investigator.	None
Grade 2 Requires infusion interruption but responds promptly to symptomatic treatment (e.g., antihistamines, NSAIDS, narcotics, IV fluids); prophylactic medications indicated for < =24 hrs	
Stop Infusion and monitor symptoms. Additional appropriate medical therapy may include but is not limited to:
 
 
IV fluids
 
Antihistamines
 
NSAIDS
 
Acetaminophen
 
Narcotics
 
 
Increase monitoring of vital signs as medically indicated until the subject is deemed medically stable in the opinion of the investigator. If symptoms resolve within one hour of stopping drug infusion, the infusion may be restarted at 50% of the original infusion rate (e.g., from 100 mL/hr to 50 mL/hr). Otherwise dosing will be held until symptoms resolve and the subject should be premedicated for the next scheduled dose.
 
Subjects who develop Grade 2 toxicity despite adequate premedication should be permanently discontinued from further trial treatment administration.
	
Subject may be premedicated 1.5h (± 30 minutes) prior to infusion of pembrolizumab (MK-3475) with:
 
Diphenhydramine 50 mg po (or equivalent dose of antihistamine).
 
Acetaminophen 500-1000 mg po (or equivalent dose of antipyretic).


Grades 3 or 4
 
Grade 3: Prolonged (i.e., not rapidly responsive to symptomatic medication and/or brief interruption of infusion); recurrence of symptoms following initial improvement; hospitalization indicated for other clinical sequelae (e.g., renal impairment, pulmonary infiltrates)
 
Grade 4: Life-threatening; pressor or ventilatory support indicated
	
Stop Infusion. Additional appropriate medical therapy may include but is not limited to:
 
 
IV fluids
 
Antihistamines
 
NSAIDS
 
Acetaminophen
 
Narcotics
 
Oxygen
 
Pressors
 
Corticosteroids
 
Epinephrine
 
 
Increase monitoring of vital signs as medically indicated until the subject is deemed medically stable in the opinion of the investigator. Hospitalization may be indicated.
 
Subject is permanently discontinued from further trial treatment administration.
	No subsequent dosing
Appropriate resuscitation equipment should be available in the room and a physician readily available during the period of drug administration.		

**4.10 Restrictions during pregnancy and lactation**

Based on its mechanism of action, KEYTRUDA can cause fetal harm when administered to a pregnant woman.

If a subject inadvertently becomes pregnant while on treatment with pembrolizumab, the subject will immediately be removed from the study. The site will contact the subject at least monthly and document the subject’s status until the pregnancy has been completed or terminated. The outcome of the pregnancy will be reported to the Sponsor and to Merck without delay and within 24 hours to the Northwestern University and within 2

working days to Merck if the outcome is a serious adverse experience (e.g., death, abortion, congenital anomaly, or other disabling or life-threatening complication to the mother or newborn).

The study investigator will make every effort to obtain permission to follow the outcome of the pregnancy and report the condition of the fetus or newborn to Northwestern University. If a male subject impregnates his female partner the study personnel at the site must be informed immediately and the pregnancy reported to the Northwestern University and to Merck and followed as described above and in Section 7.0

It is unknown whether pembrolizumab is excreted in human milk. Since many drugs are excreted in human milk, and because of the potential for serious adverse reactions in the nursing infant, subjects who are breast-feeding are not eligible for enrollment.

